8.2.2 Efficacy Assessments

The clinical outcome assessments will be collected by subjects using a handheld device with an eDiary. The handheld device will have both the episode eDiary and the daily eDiary, which will be accessible by the subject during specified periods of the study.

Study site staff will assign and provide a handheld device with the eDiary to the subject at the run-in visit (after confirming the subject's eligibility to enter the run-in period). During the run-in period, only the episode eDiary will be available to the subject. The study site staff will train the subject on how to use the handheld device (eg, turning on/off, charging, navigating screens, transmitting data, contacting the help desk for technical assistance) and complete the episodic eDiary questions. The subject will be instructed to interact with the episode eDiary for oral triptan-treated migraine attacks and to bring the handheld device to the baseline visit. At the baseline visit, the investigator will confirm if inclusion criterion 108 has been met based on the run-in eligibility report. The episode eDiary will be made available to the subject again during study weeks 13 to 16 (month 4) of the DBTP. The episode eDiary will collect the following clinical

outcome assessments for oral triptan-related migraine attacks at the subject's own physical location (eg, home):

- Date and time of start of each headache
- Date and time of end of each headache
- Worst pain severity per headache day
- Pain features and additional symptoms of migraine attack
- The most bothersome symptom (ie, nausea, vomiting, photophobia, or phonophobia) and the severity following treatment with oral triptan
- Use of oral triptan (triptan name and dosing)

Once the subject has completed the run-in period and is considered eligible to enter the baseline period, the subject will be instructed to interact with the daily eDiary every day and to bring the device to site during every study visit. The daily eDiary will collect the following clinical outcome assessments every day at the subject's own physical location (eg, home):

- Date and time of start of each headache (ie, migraine or nonmigraine headache)
- Date and time of end of each headache
- Worst pain severity per headache day
- Pain features (eg, 1-sided, throbbing, worsens with exercise/physical activity)
- Symptoms (eg, aura, nausea, vomiting, photophobia, phonophobia)

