Migraine recurrence	return of any headache of at least moderate pain intensity in patients who were pain-free at 2 hours post-dose
MMD	monthly migraine days
MSSS	Migraine Symptom Severity Score
NCT	National Clinical Trials
NRS	Numeric Rating Scale
pain relief	reduction from moderate/severe pain to mild/no pain
PCS	Pain Catastrophizing Scale
PFS	prefilled syringes
PGI-S	Patient Global Impression of Severity
PHQ-9	Patient Health Questionnaire
Q4W	every 4 weeks
QM	once monthly
Qualifying oral triptan-treated attacks (run-in period/month 4)	migraine attacks of at least moderate peak pain intensity that are treated with an oral triptan within 2 hours of pain reaching at least moderate severity
Qualifying oral triptan-treated attacks (baseline/ month 1, 2, and 3)	migraine attacks that are treated with an oral triptan
Randomization	defined as the day a subject has met all run-in and baseline period eligibility criteria and is enrolled and randomized into the study (subjects are enrolled same day)
SAP	statistical analysis plan
SC	subcutaneous(ly)

Abbreviation or Term	Definition/Explanation
Source d ata	information from an original record or certified copy of the original record containing patient information for use in clinical research. The information may include, but is not limited to, clinical findings, observations, or other activities in a clinical trial necessary for the reconstruction and evaluation of the trial. Source data are contained in source documents (original records or certified copies). (ICH Guideline [E6]). Examples of source data include Subject identification, Randomization identification, and Stratification Value.
Study d ay 1	defined as the first day that protocol-specified investigational product(s)/protocol-required therapies is/are administered to the subject
Total migraine freedom days	Days where there is an absence of headache and aura, photophobia, phonophobia, and nausea/vomiting
US	United States

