5.1.2 Efficacy Endpoints Based on Episodic Diary Data Collection During E-DBTP

During the 2-week run-in period and the 1-month E-DBTP at month 4, subjects experiencing a qualified triptan-treated migraine attack will report medication usage, pain intensity, the most bothersome symptom and corresponding severity using the episodic diary. A qualifying headache for reporting is a headache reaching at least moderate pain intensity with initial triptan intake within 2 hours and also satisfying migraine headache criteria (ie, a qualified triptan-treated migraine attack). The initial triptan intake time (ie, time point 0) will trigger a 48-hour assessment window, during which the headache pain intensity, severity of the most bothersome symptom at 30, 60 and 120 minutes, 24 hours and 48 hours post triptan will be collected. Another 48-hour assessment window will be triggered if there is a new qualified triptan-treated migraine attack starts after the previous assessment window.

Headache Pain Intensity (NRS) in E-DBTP

Worst or peak pain intensity collected on a headache ranges from 0 to 10 with a higher score indicating more severe pain.

NRS Pain intensity is collected when a qualified headache reaching at least moderate pain intensity with triptan intake within 2 hours and for the following timed assessments at 30 minutes, 1-hour, 2-hour, 24-hour and 48-hour diaries.

Migraine Rescue Medication

Migraine rescue medication for each qualifying triptan-treated attack is defined as any additional acute headache medication(s) taken during the 48-hour assessment window.

Migraine Recurrence Within 24 Hours Post-triptan

Pain intensity NRS = 0 at any of the 30-minute, 60-minute, and 2-hour timed assessments and pain intensity NRS \geq 4 at 24-hour timed assessment

Pain Relief at timed assessment post-triptan dose

Pain intensity NRS < 4 at the specific timed assessment (eg, 30 minutes, 60 minutes, or 2 hours post-triptan dose).

Pain freedom at timed assessment post-triptan dose

Pain intensity NRS = 0 at the specific timed assessment (eg, 30 minutes, 60 minutes or 2 hours post-triptan dose).

Achievement of 24-hour sustained pain freedom post-triptan dose

Pain intensity NRS = 0 at both 2-hour and 24-hour timed assessment without rescue medication taken post-triptan dose.

Most Bothersome Symptom

The most bothersome symptom can be selected among nausea, vomiting, sensitivity to light, or sensitivity to sound.

Severity of Most Bothersome Symptom (4-level)

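### The SAP's rule for migraine recurrence within 24 hours departs from the protocol's definition in two ways, neither declared: it reads the return only at the 24-hour entry, and it accepts pain freedom before 2 hours (exploratory endpoint)

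*SAP*

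**What the plan says.** Protocol Section 3 lists migraine recurrence over the 24 hours after the triptan dose, for the first qualifying attack in month 4, as an exploratory endpoint. Protocol Section 11.1 defines recurrence as "return of any headache of at least moderate pain intensity in patients who were pain-free at 2 hours post-dose".

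SAP Section 5.1.2 derives it from two conditions:

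- the pain-free condition: "Pain intensity NRS = 0 at any of the 30-minute, 60-minute, and 2-hour timed assessments";
- the return condition: an NRS of at least "4 at 24-hour timed assessment".

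There is no medication term. On the schedule, the same section says that headache pain intensity and "severity of the most bothersome symptom at 30, 60 and 120 minutes, 24 hours and 48 hours post triptan will be collected". It adds that NRS pain is collected when the qualifying headache is reported and "for the following timed assessments at 30 minutes, 1-hour, 2-hour, 24-hour and 48-hour diaries". It labels the score as worst or peak intensity but gives no recall period for the timed entries.

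The neighbouring endpoint, 24-hour sustained pain freedom, does have a medication term: "Pain intensity NRS = 0 at both 2-hour and 24-hour timed assessment without rescue medication taken post-triptan dose". Rescue medication is "any additional acute headache medication(s) taken during the 48-hour assessment window".

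Protocol Section 8.2.2 lists further episode eDiary items, including "Date and time of start of each headache", its end, and worst pain severity per headache day. The recurrence rule uses none of them. SAP Section 10 reports one deviation from the protocol, the change of efficacy analysis sets.

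**The concern.** The protocol endpoint is an event over a period. If the 24-hour NRS is current pain, the SAP measures a state at one moment: at least moderate pain at 24 hours after some earlier pain freedom. A headache that comes back at 8 hours and has settled to NRS 0–3 by 24 hours is then lost. Returns that were treated successfully are especially likely to be lost, because the rule ignores medication. How often subjects re-treat may differ between arms, so the loss need not be equal.

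The pain-free condition errs in the other direction. By accepting pain freedom at 30 or 60 minutes, it can count a recurrence in a subject who was in pain at 2 hours, whom the protocol's definition excludes.

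A published recurrence rate and odds ratio would therefore carry the protocol's name but describe something else.

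**Working it through.** The documents give no rate, power or sample size for this endpoint, so there is no planned figure to reproduce. The check has two parts.

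**1. Scoring hypothetical attacks.** Rules as in SAP Section 5.1.2, with the 24-hour NRS read as current pain:

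- Recurrence = (NRS 0 at 30 min, 60 min or 2 h) and (NRS ≥ 4 at 24 h).
- Sustained pain freedom = NRS 0 at 2 h and at 24 h, and no rescue medication.
- Protocol recurrence = NRS 0 at 2 h, and any return of at least moderate pain by 24 h.

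| Course | SAP recurrence | Protocol recurrence | SAP sustained freedom |
|---|---|---|---|
| A. Free at 2 h, returns to NRS 7, settles unaided, NRS 0 at 24 h | No | Yes | Yes |
| B. As A, but settles with rescue | No | Yes | No |
| C. Free at 2 h, returns to NRS 7, NRS 2 at 24 h, no rescue | No | Yes | No |
| D. Free at 2 h, returns, NRS 5 at 24 h | Yes | Yes | No |
| F. Free at 60 min, NRS 5 at 2 h and at 24 h | Yes | No | No |

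A, B and C are missed recurrences. F is counted against the protocol's definition, and this does not depend on reading the 24-hour entry as current pain. Sustained pain freedom fails only in A. In B the no-rescue condition catches the return, and in C the 24-hour NRS does.

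**2. Illustration of size.** Every rate here is an assumption. Take true recurrence of 30% on placebo and 20% on erenumab, and let f be the share of returns below NRS 4 by 24 h.

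- Scored rate = true rate × (1 − f), by arm.
- OR = [e/(1 − e)] / [p/(1 − p)], with e the erenumab rate and p the placebo rate.
- Power = Φ[(|p − e| − 1.96·SE₀)/SE₁], with SE₀ from the pooled proportion and SE₁ unpooled. The number per arm is 288 × 0.9 = 259.2 and the test is two-sided at 0.05.

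| f placebo | f erenumab | Scored rates, placebo / erenumab | OR | Power |
|---|---|---|---|---|
| 0 | 0 | 30% / 20% | 0.58 | 75% |
| 0.25 | 0.25 | 22.5% / 15% | 0.61 | 59% |
| 0.50 | 0.50 | 15% / 10% | 0.63 | 41% |
| 0.75 | 0.75 | 7.5% / 5% | 0.65 | 22% |
| 0.50 | 0.25 | 15% / 15% | 1.00 | no difference |
| 0.25 | 0.50 | 22.5% / 10% | 0.38 | 97% |

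Example for the third row: 0.30 × 0.5 = 0.15 and 0.20 × 0.5 = 0.10; OR = (0.10/0.90)/(0.15/0.85) = 0.63.

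A second set of assumed rates gives the same picture. With 35% and 25%, the true OR is 0.62. Detecting 50% of returns in both arms gives 17.5% and 12.5% (OR 0.67); detecting 30% gives 10.5% and 7.5% (OR 0.69).

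The power column shows only the relative loss. It treats all 259.2 subjects per arm as having an evaluable attack. If recurrence is analysed only among subjects who became pain-free, which Table 9-3 of the SAP does not state, the numbers are smaller.

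**The case against.** The strongest objection is the recall period. SAP Section 5.1.2 calls the month 4 NRS worst or peak intensity. For the daily diary, SAP Section 5.1.1 describes a later entry as rating the period since the previous diary was completed. If the 24-hour entry looks back in the same way, a return at 8 hours would be captured and the gap closes. This stands: the documents do not settle the point, so a reader who infers that recurrence within 24 hours cannot be obtained from these data goes too far. It does not make the SAP sound. If the 2-hour entry also looks back, 2-hour pain freedom would mean no pain since the 1-hour entry, which fits poorly with the SAP defining pain freedom at a specific timed assessment. Nor does recall explain course F.

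Three other stronger readings are tempting and are not supported:

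- That sustained pain freedom has the same defect. Its no-rescue condition spans the gap, so only a return that settles without medication escapes.
- That the treatment effect would be reversed. A reversal can be produced: detecting 30% of placebo returns and 50% of erenumab returns turns 35% and 25% into 10.5% and 12.5%, OR 1.22. It comes entirely from the chosen detection rates; the opposite imbalance exaggerates benefit, and equal detection barely moves the odds ratio.
- That re-treated returns vanish from the analysis. Use of rescue medication within 24 hours is a separate planned endpoint.

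It is also fair to object that recorded headache start times may not repair the rule. A new 48-hour window opens only for a new qualifying attack after the previous window, so a return inside it may generate no new start. Worst severity is kept per headache day, and a qualifying attack is already at least moderate, so a same-day value cannot separate a return from the original pain.

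**Conclusion.** Wrong as written, for an exploratory endpoint only. Two departures from the protocol's definition are undeclared. The early pain-free condition conflicts with the protocol whatever the recall period. The single 24-hour reading conflicts with it unless the 24-hour NRS asks for worst pain since the 2-hour entry.

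The size and direction of any bias are unknown. Equal under-detection mainly lowers the event rate and the power. Unequal under-detection could move the odds ratio either way. All rates used to show this are assumed.

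A reader might infer that the trial's main results are at risk. They are not: recurrence and sustained pain freedom lie outside the sequential testing procedure and the sample size calculation, and no primary or secondary conclusion changes.

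**What to change.** In SAP Section 5.1.2, before database lock:

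1. State the recall period of the 24-hour NRS item.
2. Require NRS 0 at 2 hours for recurrence, as the protocol does.
3. If the item is current pain, also count acute headache medication taken after 2-hour pain freedom and up to 24 hours as recurrence. The cut at 24 hours must be explicit, because the SAP's rescue definition runs to 48 hours. Use recorded headache times only if the sponsor confirms that the episode eDiary captures returns inside the 48-hour window.
4. Otherwise, keep the 24-hour reading and rename the endpoint: at least moderate pain at 24 hours after initial pain freedom. Declare the change in SAP Section 10.

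The cost is SAP wording and some programming. The medication term should need no new data, since rescue use within 24 hours is already a planned endpoint. The drawback of step 3 is that a dose taken for mild returning pain counts as recurrence, although the protocol's definition requires at least moderate pain.

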Ex	ploratory Double-blind Treatment Pha	se (m	nonth 4) - Continued
•	To evaluate the treatment benefit of erenumab on use of migraine rescue medication following treatment with an oral triptan	•	Use of migraine rescue medication within 24 hours post-triptan dose for the first attack at month 4
Fo as	r the first qualifying oral triptan-only-t sessment:	reate	d attack with complete data at 2-hour
•	To evaluate the treatment benefit of erenumab on achieving and sustaining pain freedom following treatment with oral triptan only	•	Achievement of pain freedom at 30, 60, and 120 minutes post-triptan dose for the first triptan-only-treated attack in which complete data is obtained (at least 2 hours timepoint) at month 4
•	To evaluate the treatment benefit of erenumab on achieving pain relief following treatment with oral triptan only	•	Achievement of pain relief at 30, 60, and 120 minutes post-triptan dose for the first triptan-only-treated attack at month 4
•	To evaluate the treatment benefit of erenumab on achieving freedom from the most bothersome symptom following treatment with oral triptan only	•	Achievement of freedom from the most bothersome symptom at 30, 60, and 120 minutes post-triptan dose for the first triptan-only-treated attack at month 4
•	To evaluate the treatment benefit of erenumab on achieving relief from the most bothersome symptom following treatment with oral triptan only	•	Achievement of relief from the most bothersome symptom at 30, 60, and 120 minutes post-triptan dose for the first triptan-only-treated attack at month 4

4. Study Design

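### Month-4 outcomes at 30, 60 and 120 minutes ignore acute medication added after the triptan, and the triptan-only attack is left undefined

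*SAP*

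**What the plan says.** The month-4 phase is meant to assess acute response to oral triptan therapy (Protocol Section 4.1; SAP Section 3.1). SAP Section 5.1.2 gives the scoring rules:

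- Pain freedom: "Pain intensity NRS = 0 at the specific timed assessment".
- Pain relief: "Pain intensity NRS < 4 at the specific timed assessment".
- Freedom from the most bothersome symptom is a severity of none at the assessment. Relief is a drop of at least one severity level.
- 24-hour sustained pain freedom needs NRS 0 at 2 and 24 hours and adds a condition: "without rescue medication taken post-triptan dose".
- Rescue medication is "defined as any additional acute headache medication(s) taken during the 48-hour assessment window", and that window opens at triptan intake: "The initial triptan intake time (ie, time point 0) will trigger a 48-hour assessment window". Medication taken before 2 hours is therefore already within the rescue definition.

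The month-4 qualifying attack in Protocol Appendix 11.1 covers "migraine attacks of at least moderate peak pain intensity that are treated with an oral triptan" within 2 hours of pain reaching moderate severity. It sets no condition on other acute drugs.

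Protocol Section 3 and SAP Section 2.1 also list a parallel set of endpoints, such as "Achievement of pain relief at 30, 60, and 120 minutes post-triptan dose for the first triptan-only-treated attack at month 4". Neither document says what makes an attack triptan-only or over what period. SAP Table 9-3, including footnote d, does not list these endpoints.

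**The concern.** Success at 30, 60 and 120 minutes depends only on the score at that moment. A subject whose triptan is not working, who takes another acute drug at 45 minutes and reports NRS 0 at 2 hours, is counted as having responded to the triptan. The sustained endpoint shows that the plan has the concept of a rescue condition but does not apply it to the earlier time points.

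Nothing later in the SAP corrects this. Non-responder imputation (Section 9.5.3, Table 9-3) applies to missing data only. The optional month-4 covariates in Section 4.1 are medication overuse, time to triptan and pain severity before the triptan; none covers added medication. Section 9.5.2 rules out sensitivity analyses for exploratory endpoints, and Section 9.5.3 plans none.

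Rescue use is itself a month-4 treatment outcome. If it differs between arms, the as-written response rates differ even when the response to the triptan is the same.

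The triptan-only set does not settle the matter while its definition is open. If a programmer borrows the 48-hour rescue window, an attack that failed at 2 hours and was medicated at 3 hours is no longer triptan-only and drops out. Attacks would then be selected on a post-randomization consequence of the outcome being measured.

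**Working it through.** The documents state no response rate, rescue rate, sample size or power for any month-4 endpoint, so there is no plan figure to reproduce. All inputs below are assumptions, used only to show how the definitions behave when the treatment has no effect.

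**As-written scoring.** Inputs:

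- p = probability of 2-hour pain freedom on the triptan alone, equal in both arms: 0.20 to 0.40.
- r = share of those not pain-free who add medication before 2 hours: 0.20 to 0.40 on placebo, half that on erenumab.
- c = chance that such a subject has NRS 0 at 2 hours: 0.2 to 0.4.

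As-written rate = p + (1 − p) × r × c. If added medication counts as non-response, the rate is p in both arms and the odds ratio is 1.00.

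Example with p = 0.30, r = 0.40 v 0.20, c = 0.4:

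- Placebo: 0.30 + 0.70 × 0.40 × 0.4 = 41.2%.
- Erenumab: 0.30 + 0.70 × 0.20 × 0.4 = 35.6%.
- Odds ratio: (0.356/0.644) / (0.412/0.588) = 0.79.

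| p | r placebo v erenumab | c | As-written rates | Odds ratio |
|---|---|---|---|---|
| 0.40 | 0.20 v 0.10 | 0.2 | 42.4% v 41.2% | 0.95 |
| 0.30 | 0.20 v 0.10 | 0.4 | 35.6% v 32.8% | 0.88 |
| 0.30 | 0.30 v 0.15 | 0.4 | 38.4% v 34.2% | 0.83 |
| 0.30 | 0.40 v 0.20 | 0.4 | 41.2% v 35.6% | 0.79 |
| 0.20 | 0.40 v 0.20 | 0.4 | 32.8% v 26.4% | 0.73 |

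The first and last rows are the extremes of the grid. Exchanging the two arms' values of r inverts each odds ratio, so the range becomes about 1.05 to 1.36. With equal rescue in both arms the odds ratio is 1.00, but both rates are inflated.

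**Triptan-only set, if it were read through the 48-hour window.** Here r is the share of failures medicated at any time in that window, a different quantity from r above. If only failures are medicated, rate = p / (p + (1 − p)(1 − r)), and with equal p the odds ratio is (1 − r placebo) / (1 − r erenumab).

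- r = 0.40 v 0.25: 0.60/0.75 = 0.80. At p = 0.30 the rates are 41.7% v 36.4%.

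That assumption is one-sided, because pain can recur after freedom and be medicated. Let s be the share of successes later medicated. The odds become p(1 − s) / [(1 − p)(1 − r)]. Keeping r = 0.40 v 0.25 and taking s = 0.30 v 0.15:

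- Odds ratio: (0.85/0.75) / (0.70/0.60) = 1.133/1.167 = 0.97.

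So even on this reading, the size depends heavily on an input that the documents do not give.

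**The case against.** Scoring regardless of added medication is a recognised treatment-policy measure. The objectives speak of response following triptan treatment, not response due to the triptan alone. The plan also has a sustained endpoint free of rescue, a separate rescue-use endpoint and a triptan-only set, all of which give context. This stands in part: it may be a deliberate choice. But the documents do not say so, and the choice sits awkwardly beside the sustained-freedom rule.

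Non-response scoring is not assumption-free either. The odds ratio of 1.00 above holds because only subjects who would not have been pain-free are assumed to add medication early. A subject who would have responded but took a second drug early would be scored as a failure. That is a reason to state the choice openly and, where needed, to show both versions.

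A reader might infer that the triptan-only set does discard attacks that failed and were then rescued. The documents do not support that. The term is undefined, the endpoints require complete data at 2 hours, and all are measured by 120 minutes. A reading based on initial treatment, or on the first 2 hours, is at least as natural, and both keep an attack medicated at 3 hours. The denominator is also unsettled. The E-DBTP set is everyone who received the week 12 dose (SAP Section 6.3), and the SAP does not make clear whether subjects with no triptan-only attack are imputed as non-responders. The supportable defect here is the missing definition.

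A reader might also take the odds ratios as estimates of bias against erenumab. They are not: neither the rescue rates nor the direction of any difference can be derived from the documents.

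Finally, intake times to 30, 60 and 120 minutes are not shown to exist. The episode eDiary list in Protocol Section 8.2.2 names only oral triptan use, and SAP Section 5.1.2 speaks generally of medication usage. This stands, and the fix depends on confirming it.

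**Conclusion.** The point holds for pain freedom, pain relief and most-bothersome-symptom freedom or relief at 30, 60 and 120 minutes. As written, acute medication added after the triptan and before the assessment does not prevent a subject from counting as a responder, and a between-arm difference in early rescue would bias the comparison. Under the assumed inputs and no true effect, with early rescue twice as common on placebo, the pain-freedom odds ratio is 0.73 to 0.95. This illustrates the mechanism and is not an estimate.

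For the triptan-only endpoints, the finding is that a key term lacks a definition and that one available reading would select attacks on a consequence of the outcome. The plan does not prescribe that reading.

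All these endpoints are exploratory and outside the sequential testing procedure, so no primary or secondary conclusion is affected. The change is worth making because response to the triptan is a main purpose of month 4.

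**What to change.** Before unblinding, amend SAP Section 5.1.2:

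1. Confirm that the episode diary records acute medication intake finely enough to place it before or after each timed assessment and before or after the initial triptan.
2. For pain freedom, pain relief and most-bothersome-symptom freedom or relief, count a subject who took any additional acute headache medication between the initial triptan and a timed assessment as a non-responder at that and later timed assessments.
3. If scoring regardless of added medication was intended, say so and report the version in step 2 alongside it.
4. Define a triptan-only-treated attack by medication taken up to triptan intake. Keep attacks with later added medication in the set, and score medication added before an assessment as non-response. Add these endpoints to Table 9-3, including how subjects with no such attack are handled.

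This concerns scoring only and changes nothing about what subjects may take. If step 1 is satisfied, the cost is SAP wording and derivation. The downside is slightly lower reported response rates.

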 To evaluate the treatment benefit of erenumab on functional impairment 	 Change from baseline in headache impact scores as measured by the Headache Impact Test (HIT-6) total score at assessment time points
	 Change from baseline in physical function domain score as measured by MFIQ at assessment time points
	 Change from baseline in usual activities domain score as measured by MFIQ at assessment time points
	 Change from baseline in social function domain as measured by MFIQ at assessment time points
	 Change from baseline in emotional function domain score as measured by MFIQ at assessment time points
	 Change from baseline in overall impact on usual activities global

	1
	item score as measured by MFIQ at assessment time points
 To evaluate the treatment benefit of erenumab on headache-related cognitions and beliefs 	 Change from baseline in pain catastrophizing as measured by the Pain Catastrophizing Scale (PCS) at month 3
 To evaluate the treatment benefit of erenumab on monthly migraine days (MMD) 	Change from baseline in mean MMD over months 1, 2, and 3
Following 2 endpoints will be calculated attack	from months with at least 1 migraine
• To evaluate the treatment benefit of erenumab on duration of migraine pain of at least moderate intensity with at least 1 migraine attack	Change from baseline in mean monthly average duration of at least moderate pain intensity per migraine attack occurring over months 1, 2, and 3
 To evaluate the treatment benefit of erenumab on peak migraine pain intensity with at least 1 migraine attack 	Change from baseline in mean monthly average peak migraine pain intensity as assessed by the 11-point Numeric Rating Scale (NRS) over months 1, 2, and 3
Exploratory Double-blind Treatment Phase	
To evaluate the treatment benefit of erenumab on interictal burden of migraine	• Change from baseline in Migraine Interictal Burden Scale (MIBS-4) total score at month 4
For the first qualifying oral triptan-treated assessment:	d attack with complete data at 2-hour
To evaluate the treatment benefit of erenumab on achieving and sustaining pain freedom following treatment with an oral triptan	 Achievement of pain freedom at 2 hours post-triptan dose for the first attack at month 4 Achievement of 24-hour sustained pain freedom post-triptan dose for the first attack at month 4
	 Achievement of pain freedom at 30 and 60 minutes post-triptan dose for the first attack at month 4

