9.5.3 E-DBTP Analyses of Exploratory Efficacy Endpoints

The dichotomous efficacy endpoints for assessing qualifying triptan-treated attacks only in E-DBTP will be analyzed using logistic regression model with missing data imputed as non-responders (NRI) **up to End of Study Date**. Odds ratios of treatment group and placebo with associated 95% CIs and p-values will be reported. The efficacy endpoint for Migraine Interictal Burden Scale at month 4 will be analyzed using the linear mixed effects model that includes treatment group, baseline values, scheduled visit, and the interaction of treatment and scheduled visit without any imputation for missing data.

The following exploratory endpoints of the E-DBTP for the first qualifying triptan-treated attack will be analyzed by medication overuse status at month 3 (yes vs. no):

- Achievement of pain freedom at 2 hours post-triptan dose for the first attack at month 4
- Achievement of pain relief at 2 hours post-triptan dose for the first attack at month 4
- Achievement of relief from the most bothersome symptom at 30, 60, and 120 minutes post-triptan dose for the first attack at month 4
- Achievement of 24-hour sustained pain freedom post-triptan dose for the first attack at month 4
- Migraine recurrence within 24 hours post-triptan dose for the first attack at month 4
- Use of migraine rescue medication within 24 hours post-triptan dose for the first attack at month 4

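### The exploratory 24-hour sustained pain freedom endpoint puts no 24-hour limit on its rescue condition, so read literally medication taken at 24-48 hours makes a subject a non-responder

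*SAP*

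**What the plan says.** The endpoint is listed in SAP 2.1 as "Achievement of 24-hour sustained pain freedom post-triptan dose for the first attack at month 4". SAP 5.1.2 defines it as "Pain intensity NRS = 0 at both 2-hour and 24-hour timed assessment without rescue medication taken post-triptan dose". The rescue condition is the closing clause, "without rescue medication taken post-triptan dose", which states no end time.

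The term rescue medication has its own definition in the same section: "Migraine rescue medication for each qualifying triptan-treated attack is defined as any additional acute headache medication(s) taken during the 48-hour assessment window". The window is anchored at the first triptan: "The initial triptan intake time (ie, time point 0) will trigger a 48-hour assessment window". A later attack opens its own window only once the first has closed: "Another 48-hour assessment window will be triggered if there is a new qualified triptan-treated migraine attack starts after the previous assessment window".

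The companion endpoint on rescue use carries an explicit limit. SAP 9.5.3 lists it as "Use of migraine rescue medication within 24 hours post-triptan dose for the first attack at month 4", and SAP 2.1 and Table 9-3 give the same 24-hour limit.

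The sustained endpoint is analysed by logistic regression with missing data scored as non-response (Table 9-3 footnote d and SAP 9.5.3), and also by medication overuse status at month 3. Neither place adds a time limit to the rescue condition. The protocol (Section 3) gives the endpoint the same 24-hour name and does not define rescue medication.

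**The concern.** The two halves of the definition cover different periods. The pain condition ends at 24 hours. The medication condition, through the defined term, runs to 48 hours. A subject with untreated severe pain at 30 hours stays a responder, while a subject who takes a simple analgesic at 30 hours becomes a non-responder. A 24-hour outcome should not depend on what happens on the second day.

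Month 4 is meant to show whether erenumab improves the acute response to an oral triptan. Under the literal rule the result also depends on how often subjects take acute medication in the following 24 hours. That can dilute a real difference or create an apparent one. The share of subjects affected may also differ between the medication overuse subgroups in which the endpoint is analysed, because most of the overuse criteria require 10 or more medication days a month.

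**Working it through.** The plan gives no rate, sample size or power for this endpoint, so there is no figure to reproduce. The check has three parts.

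**1. The rule applied case by case.** Take a subject with a pain score of 0 at 2 h and at 24 h, and vary the time of the first additional acute headache medication.

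| Time of medication | SAP text (rescue counted over 0-48 h) | Rescue limited to 24 h |
|---|---|---|
| none | responder | responder |
| 5 h or 23 h | non-responder | non-responder |
| 25 h, 40 h or 47 h | non-responder | responder |
| 49 h | responder | responder |

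The two rules differ only for medication taken after 24 h and up to 48 h.

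**2. Equal late-medication shares.** Let p be the true 24-hour response rate and f the share of true responders who take medication at 24-48 h. The observed rate is p × (1 − f). The documents give neither p nor f. Assume p = 25% on placebo and 35% on erenumab, with the same f in both arms:

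| f (assumed) | Placebo | Erenumab | Difference (true value 10.0 points) |
|---|---|---|---|
| 5% | 23.75% | 33.25% | 9.5 |
| 10% | 22.5% | 31.5% | 9.0 |
| 20% | 20.0% | 28.0% | 8.0 |
| 30% | 17.5% | 24.5% | 7.0 |

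A true benefit is diluted.

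**3. Unequal shares with no true effect.** Assume p = 20% in both arms. The odds ratio compares erenumab with placebo.

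- f = 10% placebo, 5% erenumab: 0.20 × 0.90 = 0.18 and 0.20 × 0.95 = 0.19. Odds ratio (0.19/0.81) / (0.18/0.82) = 1.07.
- f = 30% placebo, 20% erenumab: 0.20 × 0.70 = 0.14 and 0.20 × 0.80 = 0.16. Odds ratio (0.16/0.84) / (0.14/0.86) = 1.17.
- An intermediate case uses the one between-arm figure in the documents, the difference of 1.85 monthly migraine days for 140 mg in Study 20120296 (protocol 2.3). If every migraine day were medicated and days were evenly spread, 1.85/28 = 6.6 percentage points per 24 hours. With f = 30% and 23.4%, the rates are 14.0% and 15.3% (0.20 × 0.766 = 0.1532), odds ratio about 1.11.

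If the shares were reversed between arms, the odds ratios would be the reciprocals: 1/1.07 = 0.93 and 1/1.17 = 0.85.

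**The case against.** **The endpoint name implies 24 hours.** A programmer could carry the 24-hour horizon in the name over to the medication condition and never produce the misclassification. That is possible, and the sponsor may have meant it. But the clause uses a term that the same section defines over 48 hours, and the companion endpoint shows the limit being written where it is wanted. The text should not depend on a programmer's inference.

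**Recurrence within 48 hours is the same attack.** Protocol 11.1, and SAP 5.1.1 for months 1 to 3, count a migraine that returns within 48 hours of attack start as one attack. Medication at 30 hours would then often be for a relapse, so the rescue condition could be seen as picking up a genuine failure. This does not bring the second day into a 24-hour outcome, since pain in that period is not scored. It does weaken one argument about bias. A reader might infer that the flaw turns fewer migraine days on erenumab into an apparently better triptan response. That requires the late medication to be for independent new attacks and its share to be higher on placebo. The documents establish neither.

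**The consequence is small.** This stands. The endpoint is exploratory, has no power statement and is outside the sequential testing procedure. Even 14% vs 16%, with all 259 subjects per arm (288 × 0.9) contributing, gives z of about 0.6: 0.02 / √(2 × 0.15 × 0.85 / 259) = 0.02/0.031.

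**Conclusion.** The point holds as a flaw in the definition. Taken as written, SAP 5.1.2 makes a subject who met the 24-hour outcome a non-responder for medication taken at 24-48 hours. This follows from the SAP's own defined term and needs no assumption about rates.

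The size and direction of the effect on the treatment comparison are unknown. Every rate in the illustrations is assumed. Equal late-medication shares of 5-30% would take a true 10-point difference down to 9.5-7.0 points. Shares higher on placebo would give an odds ratio of about 1.07 to 1.17 with no true effect. A reader might take the upper figure as evidence of bias towards erenumab. The documents do not support that, because the result changes sign or becomes dilution under other equally unverified shares.

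Primary and secondary conclusions are unaffected. This is a minor correction.

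**What to change.** In SAP 5.1.2, insert the words *within 24 hours* before *post-triptan dose* in the rescue condition of the sustained pain freedom definition. The pain condition and the 48-hour definition of rescue medication can stay as they are. Make the change before unblinding, so that the choice of rule cannot appear to depend on the results.

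The cost is one phrase in the SAP and a matching programming specification. No new data should be needed, because the companion endpoint already requires rescue use to be placed within 24 hours of the triptan. One check is worthwhile: the episode eDiary list in protocol 8.2.2 mentions only triptan name and dosing, so confirm that the diary records the time of any additional medication. If it does not, the companion endpoint has the same difficulty.
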